1. OBJECTIVES

The objectives of our study are the following:

General:

- Determine the effectiveness of a protocolized treatment of specific physiotherapy for patients undergoing femoroacetabular syndrome by means of arthroscopy in pain, range of mobility and functionality.

Specific:

- Check how the age, level of physical activity prior to the study, sex, level of adherence to the program or body mass index of the subject influences the effectiveness of protocolized treatment of physiotherapy in patients surgically operated on femoroacetabular syndrome by arthroscopy.

2. STUDY DESIGN

An analytical, longitudinal, experimental, prospective, controlled and randomized clinical study will be conducted to analyze the cause-effect relationship of the Müller & Puig physiotherapy protocol under study in relation to the change in pain, functionality (modified Harris scale) and the range of mobility (ROM) in subjects surgically operated by Femoro-acetabular Impingement (FAI) by arthroscopy.

The study will be simple blind with blinded evaluator strategy with two parallel groups. The surgeons (recruitment) and assessors will be blinded with respect to the group belonging to the subject. The statistician will be blinded to the subjects group until the statistical analysis is completed. It is not possible to blind the physiotherapist who executes the treatment protocol or the study subjects. Subjects will be asked not to disclose their membership group or consult with the surgeon or the evaluator.

The randomization approach will be prepared by means of a randomization computer program, attributing a 1:1 ratio to the membership group. The interventionist physiotherapist will perform the randomization on the day of the first post-surgery physiotherapy session.

All participants will be informed of the purpose of the study through an information document prepared for this purpose and will be clarified any doubts that may arise. After answering as many questions as necessary, the subject must sign the informed consent document to be part of the study. The principles of the Declaration of Helsinki (2004) will

be respected at all times. The data collected will be treated confidentially by applying the current legislation on the protection of personal data (Organic Law 15/1999 of December 13, Protection of Personal Data) and / or any other applicable.

This study has been admitted by the Research and Ethics Committee of General University Hospital of Elche PI 6/2019.

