4. INTERVENTION PROTOCOL

The intervention consists of a physiotherapy treatment protocol for post-surgical treatment of CFA under arthroscopy. This protocol is based on the existing ones to date of the various specialists in arthroscopic surgery, which propose rehabilitative actions of a general type, divided into four phases. The results of this group will be compared to those obtained in the control group that will follow the usual post-surgical general guidelines for hip interventions described by Gocen et al.

The intervention is structured in 14 weeks as described below.

Day 1 to 7:

- Isometric quadriceps contractions (4 sets of 10 repetitions twice a day)
- Isometric contractions of the vast internal (4 sets of 10 repetitions twice a day)
- Flexo-extension and ankle circumduction movements (4 sets of 10 repetitions twice a day)
- Hip flexion in supine trailing heel by stretcher (4 sets of 10 repetitions 2 times a day)
- Passive hip circumduction (2 series of 5 minutes a day)
- Ambulation with two crutches without load on the lower limb affected
- Stay in prone position (2 hours a day)
- Stay in a sitting position at 90 degrees of hip flexion (2 hours a day).
- Half-lying between 90 and 180 degrees (2 hours a day).
- Keep the hip in neutral rotation position.

Day 8 to 15:

It is added to the previous guideline:

- Patient in prone position and extension of hip with knee in full extension (4 sets of 10 repetitions once a day)
- Patient in prone position and extension of hip with knee in flexion of 45° (4 sets of 10 repetitions once a day)
- Patient in prone position and extension of hip with knee in 90° flexion (4 sets of 10 repetitions once per day)
- Patient sitting and full knee extension (4 sets of 10 repetitions once a day)

Day 16 to 21:

To the pattern of the first week we add the following:

- Patient in prone position and extension of hip with knee in full extension with resistance in ankle with elastic band of 1.5 m in length and soft resistance (4 sets of 10 repetitions once a day)

- Patient in prone position and extension of hip with knee in flexion of 45° with resistance in ankle with elastic band of 1.5 m of length and soft resistance (4 sets of 10 repetitions once a day)
- Patient in prone position and hip extension with knee in 90° flexion with resistance in the ankle with an elastic band of 1.5 m in length and soft resistance (4 sets of 10 repetitions once a day)

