The sample will be divided into 2 groups: Intervention Group and Control Group. The postoperative physiotherapeutic treatment protocol described will be applied to the intervention group. The non-intervention group will receive the nonspecific protocol of postoperative treatment for hip rehabilitation described by Gocen et al.

7. EVALUATION.

The evaluator is the person who will perform the pre and postsurgical measurements. He will be trained in the use of the goniometer and in the performance of orthopedic tests as well as in the material to be used. It will be located in the "Evaluation Room", with the material and conditions necessary to carry out the measurements. It will register and store the data for its later evaluation and statistical analysis.

The evaluator will be blinded with respect to the subject's belonging to the intervention or control group.

Data will be recorded at three times: before surgery, after 4 weeks and after 14 weeks of surgery. Immediate postoperative measurements will not be made, given that the clinical picture and tissue injury of the intervention could cause inaccurate results because a period of post-surgical wound stabilization has not elapsed.

These tests and measurements of variables will provide us with the degree of hip readjustment and its functionality, since they respond to the affected musculoskeletal structures both prior to the arthroscopy intervention due to the pathophysiology of the FAI, and after it for the wounds and surgical scars that are generated.

8. STUDY SEQUENCE.

A. Recruitment: it takes place before the surgery in the Traumatology clinic of Alicante Clinic (we attach authorization of the center to carry out the study) Two facultative specialists in orthopedic surgery and traumatology, transfer the information to the patient in written support about the characteristics of the study , purpose and form of follow-up, at the same time that they verify the eligibility of the subject according to the criteria of the study. Another member of the research team will independently check the eligibility of the subject in an evaluation session and will be responsible for performing the evaluations of the study variables before surgery, at 4 and 14 weeks after surgery. The evaluator will be present to resolve and clarify any doubts in this regard. After this, and with the acceptance of the patient to be part of the study, the informed consent will be signed.

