B. Pre-surgery evaluation: the Harris scale questionnaire modified prior to the surgical procedure will be completed. After signing the informed consent, the pre-surgical measurement will be carried out following the following sequence:

- Assessment tests of abduction, adduction, flexion, extension, internal rotation and external rotation ROM of the hip
- Next, the Ober, Fabere and Faddir muscle tests will be performed.
- Finally, the pain will be evaluated through the Visual Analog Scale (VAS)

C. Randomization: After the presurgical evaluation and following a simple randomization process by means of a computer program, the subjects are assigned to the control or intervention group.

D. Hip arthroscopy: The study subjects will receive adequate pre- and postoperative care including health education and exercise plan for the immediate postoperative period, in addition to a follow-up visit by the traumatologist after two weeks of the intervention.

E. Intervention: The subjects of the control group follow the general postsurgical treatment protocol described by Gocen et al. The subjects of the intervention group will perform a physiotherapy session of 45 minutes each one every two weeks for a total of 7 sessions (weeks 2, 4, 6, 8, 10, 12 and 14 post surgery) following the protocol described. In addition, they will have to follow a physiotherapy exercise plan at home whose compliance they will have to register in an activity diary to check adherence to treatment.

F. Post-surgery evaluation 1: The evaluation described in section B and C is repeated 4 weeks after surgery to subjects of both groups.

G. Post-surgery evaluation 2: The evaluation described in section B and C is repeated after 14 weeks of the surgery for the subjects of both groups, and the individual study is finished.

In both groups, it will be advised to avoid stairs, ramps, squats, forced hip flexion and legs crossing in all phases. The subjects that develop a deterioration in the Modified Harris scale or in the VAS at 4 weeks after surgery compared with the pre-surgical data or those subjects that reflect complications of the surgery will be evaluated again by their corresponding traumatologist to decide whether or not to remain in the program. All complications will be documented by the principal investigator. No adverse effects are expected.

Statistical Analysis Plan (SAP)

Size Sample and Feasibility

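### Sections 2 and 8 put randomisation at two different points, unreconciled, and section 2's trigger has no date for control patients in these documents

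*Combined protocol and SAP*

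**What the plan says.** Section 2 (Study design) gives the rule on timing and operator: "The interventionist physiotherapist will perform the randomization on the day of the first post-surgery physiotherapy session". The same section says that the physiotherapist who delivers the treatment cannot be blinded, and that a computer program prepares a 1:1 allocation.

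Section 8 (Study sequence) is a lettered list: A recruitment, B presurgical evaluation, C randomisation, D arthroscopy, E intervention, F and G evaluations at 4 and 14 weeks. Step C reads: "After the presurgical evaluation and following a simple randomization process by means of a computer program, the subjects are assigned" to one group or the other. It names no operator and does not mention a physiotherapy session.

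Step D describes early care without separating the groups: "The study subjects will receive adequate pre- and postoperative care including health education and exercise plan for the immediate postoperative period". Step E dates sessions for one group: "The subjects of the intervention group will perform a physiotherapy session of 45 minutes each one every two weeks", seven in all, on even weeks from 2 to 14. For controls, section 6 says: "The non-intervention group will receive the nonspecific protocol of postoperative treatment for hip rehabilitation", with the content given by citation. No control session is dated.

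Section 4 says of the experimental programme: "The intervention is structured in 14 weeks as described below". Its first block is Day 1 to 7 and its last is Day 76 to 97.

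The SAP does not say which patients are analysed. No section describes how an assignment is released.

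**The concern.** The moment of randomisation fixes the population whose comparison randomisation protects. The protocol gives two moments. A patient who drops out between the presurgical evaluation and the first physiotherapy session is a post-randomisation loss if allocation happens at step C, and was never randomised if it happens at that session. Because the SAP names no analysis population, nothing downstream settles the denominators.

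Two practical difficulties follow if section 2 governs. Its trigger is an event that the documents date only for patients already in the intervention group, so staff cannot read from the protocol when a future control is to be randomised. In addition, a programme with content from day 1 cannot be delivered by group until groups exist.

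Section 2 also gives the act of randomising to the person who will deliver the treatment. Without a described release step, nothing written prevents an assignment from being delayed, repeated or changed.

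**Working it through.** The plan has no figure of its own to reproduce. The check compares the passages and adds one conditional day count.

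**1. Timing.**
- Section 2: the day of the first physiotherapy session after surgery. Allocation is therefore after surgery.
- Section 8 step C: after the presurgical evaluation. The words set an earliest time only. Allocation before surgery is inferred from C standing between B and D.
- No text links the two. Reading step C as mere preparation of a list does not fit well, because it speaks of patients being assigned.

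**2. Operator.** Section 2 names the treating physiotherapist and step C names nobody. The conflict is therefore about when, not about who.

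**3. Date of the trigger, by group.**
- Intervention: the first listed session is in week 2 (step E).
- Control: no session is dated in sections 4, 6 or 8. The cited source may schedule some, but it is not reproduced.

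**4. What precedes each allocation time.** Recruitment, eligibility, consent and baseline measurement (steps A and B) are complete before either one.

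**5. Day count if section 2 governs.** Assumptions:
- (a) Section 2's first session is step E's week-2 session.
- (b) Programme days count from surgery. This is plausible, since 14 × 7 = 98 days and the last programme day is 97, but it is not stated.
- (c) Week 2 means postoperative days 8 to 14.

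Programme days before allocation = allocation day − 1:
- Earliest: 8 − 1 = 7 days.
- Latest: 14 − 1 = 13 days.
- If week 2 instead means exactly two weeks after surgery (day 14), only the 13 applies.

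In each case the whole Day 1 to 7 block, with its 10 listed items, precedes allocation. If (a) fails because an earlier physiotherapy contact counts as the first session, the figure falls towards 0. If allocation precedes surgery, as the order in section 8 suggests, it is 0. These are calendar days, not days of shown lost contrast.

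**6. Patients affected.** This would be the number randomised × the proportion lost between the two allocation times. The documents give neither. Around 30 per group is a feasibility estimate, and the sample size is to come from a pilot. The 10 pilot subjects are all placed in one group and may be kept in the final sample, so not everyone in the total need have been randomised. No loss rate is given. No count follows.

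**The case against.** The strongest reply is that there is one explicit rule and one loose description. Section 2 names a clear trigger, while step C says only that assignment follows the presurgical evaluation, which a post-surgery date also satisfies. On that view section 2 governs and section 8 needs tidying. This stands in part: section 8 does not say that allocation precedes surgery, and a reader who infers a flat contradiction in words goes beyond the text. What remains is that the only step-by-step sequence lists assignment ahead of the operation and nothing tells staff to override that order.

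A reader might also infer that controls have no randomisation rule at all. The documents do not support that. Under section 2 nobody has a group until the session, so the trigger can be meant for every patient. The gap is narrower: no session date for controls appears here.

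A third tempting inference is that the treating physiotherapist's role, or the early days before allocation, biases the comparison or shrinks the difference between groups. Neither is shown. Baseline is complete beforehand, control content is given only by citation, and step D's early exercise plan is not split by group. Part of the calendar problem is also separate: section 4 begins on day 1 while the sessions in step E begin in week 2, and that needs explaining whichever allocation time applies.

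Finally, step F says "The evaluation described in section B and C is repeated 4 weeks after surgery to subjects of both groups", and step G does likewise at 14 weeks, although step C is randomisation. This is a clerical slip, and nothing suggests that patients are to be randomised again.

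**Conclusion.** The point holds as a defect that should be fixed. Two unreconciled descriptions of when patients are randomised give different randomised populations, and the trigger in section 2 is undated for controls in these documents. That much rests on the text, with the qualification that allocation before arthroscopy comes from step order only.

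The consequence for early treatment is conditional. If section 2's first session is step E's week-2 session and programme days run from surgery, the first seven-day block precedes allocation, and 7 to 13 programme days in all if week 2 means days 8 to 14. Neither of the first two assumptions is confirmed in the documents. The number of patients whose status would change cannot be stated. The absence of a release step leaves assignments open to interference by the person delivering treatment, but nothing indicates that interference would occur.

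**What to change.** - State one allocation time in sections 2 and 8, identical for both groups: after the presurgical evaluation and before care first differs between them.
- Release each assignment from a list generated in advance, through a locked program or sealed opaque envelopes, and only after the patient has been logged, so that the treating physiotherapist cannot delay, repeat or change it.
- State in the SAP that all randomised patients are analysed in their assigned group.
- While editing section 8, correct the cross-reference in steps F and G so that it points to the evaluation alone.
- The investigators must reconcile the treatment calendars in section 4 and in section 8 steps D and E. No view is taken here on which is right.

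The cost is protocol and SAP wording plus a locked list or envelopes, with no extra patients. The small downside is that, if allocation precedes surgery, a few allocated patients may not go on to treatment and will still count in the analysis.

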3. SUBJECTS OF STUDY

The selection criteria of the sample in this study are as follows.

3.1. Inclusion criteria

- a. Having suffered hip / groin pain for at least 3 months.
- b. Be a patient diagnosed with femoroacetabular syndrome by an orthopedic surgeon based on symptoms, clinical signs and diagnostic imaging.
- c. To have signed the informed consent.
- d. Have time available to follow a 14-week physiotherapy treatment program.
- e. Be programmed for hip arthroscopy.
- f. Be able to speak and understand the Spanish language.
- g. Be between 18 and 50 years of age.

3.2. Exclusion criteria

- a. Have received physiotherapy treatment in the last three months.
- b. Having previously received hip surgery.
- c. Subjects with previous deformities in the femur that severely alter joint mobility such as Perthes disease, gliding of the upper femoral epiphysis or avascular necrosis, acetabular fracture, hip dislocation or fracture of the femoral neck.
- d. Evidence of preexisting osteoarthritis, defined as Tonnis grade > 2
- e. Subjects with previous deformities in the pelvis that severely alter joint mobility.
- f. Any other cardiovascular, psychological and / or cognitive diagnosed pathology that impedes the correct understanding of the study and prevents objective study variables.
- g. Subjects that are under the effects of anesthetics or muscle relaxants that mask the sensation of the patient before the techniques of the study.
- h. Professional athletes.
- i. Subjects in which hip arthroscopy is contraindicated.

4. INTERVENTION PROTOCOL

The intervention consists of a physiotherapy treatment protocol for post-surgical treatment of CFA under arthroscopy. This protocol is based on the existing ones to date of the various specialists in arthroscopic surgery, which propose rehabilitative actions of a general type, divided into four phases. The results of this group will be compared to those obtained in the control group that will follow the usual post-surgical general guidelines for hip interventions described by Gocen et al.

The intervention is structured in 14 weeks as described below.

Day 1 to 7:

- Isometric quadriceps contractions (4 sets of 10 repetitions twice a day)
- Isometric contractions of the vast internal (4 sets of 10 repetitions twice a day)
- Flexo-extension and ankle circumduction movements (4 sets of 10 repetitions twice a day)
- Hip flexion in supine trailing heel by stretcher (4 sets of 10 repetitions 2 times a day)
- Passive hip circumduction (2 series of 5 minutes a day)
- Ambulation with two crutches without load on the lower limb affected
- Stay in prone position (2 hours a day)
- Stay in a sitting position at 90 degrees of hip flexion (2 hours a day).
- Half-lying between 90 and 180 degrees (2 hours a day).
- Keep the hip in neutral rotation position.

Day 8 to 15:

It is added to the previous guideline:

- Patient in prone position and extension of hip with knee in full extension (4 sets of 10 repetitions once a day)
- Patient in prone position and extension of hip with knee in flexion of 45° (4 sets of 10 repetitions once a day)
- Patient in prone position and extension of hip with knee in 90° flexion (4 sets of 10 repetitions once per day)
- Patient sitting and full knee extension (4 sets of 10 repetitions once a day)

Day 16 to 21:

To the pattern of the first week we add the following:

- Patient in prone position and extension of hip with knee in full extension with resistance in ankle with elastic band of 1.5 m in length and soft resistance (4 sets of 10 repetitions once a day)

- Patient in prone position and extension of hip with knee in flexion of 45° with resistance in ankle with elastic band of 1.5 m of length and soft resistance (4 sets of 10 repetitions once a day)
- Patient in prone position and hip extension with knee in 90° flexion with resistance in the ankle with an elastic band of 1.5 m in length and soft resistance (4 sets of 10 repetitions once a day)
- Patient sitting and full knee extension with resistance in the ankle with elastic band 1.5 m long and soft resistance (4 sets of 10 repetitions once a day)

Day 22 to 30:

- Passive hip circumduction (2 series of 5 minutes once a day)
- Walking with a crutch.
- Stay in a sitting position at 90 degrees of hip flexion (2 hours a day).
- Half-lying between 90 and 180 degrees (2 hours a day).
- Keep the hip in neutral rotation position.
- Stationary bicycle with elevated saddle and with no resistance for 15 minutes.
- Patient in prone position and extension of hip with knee in full extension with resistance in the ankle with an elastic band of 1.5 m in length and medium resistance (4 sets of 10 repetitions once a day)
- Patient in prone position and extension of hip with knee in flexion of 45° with resistance in the ankle with an elastic band of 1.5 m of length and medium resistance (4 sets of 10 repetitions once a day)
- Patient in prone position and hip extension with knee in 90° flexion with resistance in the ankle with an elastic band of 1.5 m length and medium resistance (4 sets of 10 repetitions once a day)
- Patient in sitting position and full knee extension with resistance in the ankle with an elastic band of 1.5 m length and medium resistance (4 sets of 10 repetitions once a day)

Day 31 to 45:

- Walking with a crutch.
- Keep the hip in neutral rotation position.
- Static bike with elevated saddle and with zero resistance for 25 minutes.
- Patient in prone position and extension of hip with knee in full extension with resistance in the ankle with an elastic band of 1.5 m in length and medium resistance (4 sets of 15 repetitions once a day)

- Patient in prone position and extension of hip with knee in flexion of 45° with resistance in ankle with an elastic band of 1.5 m of length and medium resistance (4 series of 15 repetitions once a day)
- Patient in prone position and hip extension with knee in 90° flexion with resistance in the ankle with an elastic band of 1.5 m length and medium resistance (4 sets of 15 repetitions once a day)
- Patient sitting and full knee extension with resistance in the ankle with an elastic band of 1.5 m in length and medium resistance (4 sets of 20 repetitions once a day).

Day 46 to 60:

- Walking without crutches
- Static bike with elevated saddle and zero resistance for 25 minutes (3 times a week)
- Activity in elliptical movement machine with minimum intensity for 15 minutes (twice a week)
- Soft proprioception exercises on an unstable base (Bosu® type) with both legs for 6 sets of 20 seconds with unlocked hips and knees.
- Standing patient, hip extension with knee in full extension with resistance in the ankle with an elastic band of 1.5 m in length and medium resistance (4 sets of 15 repetitions once a day)
- Standing patient, hip extension with knee in flexion of 45° with resistance in the ankle with an elastic band of 1.5 m in length and medium resistance (4 sets of 15 repetitions once a day)
- Standing patient, hip extension with knee in 90° flexion with resistance in the ankle with an elastic band of 1.5 m in length and medium resistance (4 sets of 15 repetitions once a day)
- Patient sitting and full knee extension with resistance in the ankle with an elastic band 1.5 m long and medium resistance (4 sets of 20 repetitions once a day)

Day 61 to 75:

- Static bike with elevated saddle and with 20% resistance for 25 minutes. (3 times a week).
- Activity in elliptical movement machine with minimum intensity for 20 minutes. (3 times a week).
- Gentle proprioception exercise on an unstable base (Bosu® type) with leg affected for 6 sets of 20 seconds with unlocked hips and knees.
- Standing patient, hip extension with knee in full extension with resistance in the ankle

with an elastic band of 1.5 m in length and medium resistance (4 sets of 15 repetitions once a day)

- Standing patient, hip extension with knee in flexion of 45° with resistance in the ankle with an elastic band of 1.5 m in length and medium resistance (4 sets of 15 repetitions once a day)
- Standing patient, hip extension with knee in 90° flexion with resistance in the ankle with an elastic band of 1.5 m in length and medium resistance (4 sets of 15 repetitions once a day)
- Patient sitting and full knee extension with resistance in the ankle with an elastic band of 1.5 m in length and medium resistance (4 sets of 20 repetitions once a day).

Day 76 to 97:

- Static bike with elevated saddle and with 20% resistance for 25 minutes. (3 times a week).
- Activity in elliptical movement machine with minimum intensity for 20 minutes. (3 times a week).
- Exercise of proprioception on an unstable basis (Bosu® type) with leg affected for 3 sets of 20 seconds with unlocked hips and knees and using an elastic band 1.5 m long and medium resistance in each of the four positions to adopt.
- Floating in a pool for 15 minutes (once a week)
- Standing patient, hip extension with knee in full extension with resistance in the ankle with an elastic band of 1.5 m in length and medium resistance (4 sets of 10 repetitions twice a day)
- Standing patient, hip extension with knee in flexion of 45° with resistance in the ankle with an elastic band of 1.5 m in length and medium resistance (4 sets of 10 repetitions twice a day)
- Standing patient, hip extension with knee in 90° flexion with resistance in the ankle with an elastic band of 1.5 m in length and medium resistance (4 sets of 10 repetitions twice a day)
- Patient sitting and full knee extension with resistance in the ankle with an elastic band of 1.5 m in length and medium resistance (4 sets of 15 repetitions twice a day).
- Basic stretching of quadriceps, hamstrings, adductor and abductor (3 times a week).

Avoid climbing stairs, ramps, squats, forced hip flexion and crossing legs in all phases.

To check the adherence to the treatment, measures based on self-report of the subject

will be used since they are the easiest to obtain and the most frequently used to measure the adherence. The measuring instrument used will be the completion of a diary design for this purpose. It will be used to monitor the performance and duration of the protocol exercises. Through the data obtained in this diary, the overall percentage of therapeutic adherence on the recommended behavior will be determined. This system acts as a reminder increasing the probability of compliance with the work plan.

